Based on available literature and our pilot data (shown below), **we hypothesize that insulin resistance (IR) and decreased cardiac fitness are central to the NAFLD in adolescents, and the degree of steatosis is negatively correlated with lower fitness and higher IR. Thus, exercise-driven improvements in IHTG levels will be positively associated with the increase in fitness and the decrease in IR levels in adolescents with NAFLD.** We will test our hypotheses through the following specific aims:

Aim 1: Assess the change in IHTG, and CVD and IR markers in subjects with NAFLD after 4 weeks of HIIT, compared to a sex-matched control group also with NAFLD with no training.

1A. Quantitate the change in IHTG. Hypothesis: IHTG will decrease after HIIT, and the change will be greater than that seen in controls.

1B. Measure the changes in fitness and markers of CVD. Hypothesis: HIIT will significantly increase fitness, decrease heart rate variability and blood pressure, and improve atherogenic lipid profile. The changes will be greater than that seen in controls. Changes in fitness and IHTG will correlate.

1C. Estimate changes on IR. Hypothesis: HIIT will decrease IR especially in those with higher baseline IR, and the changes will be greater than that seen in controls. Changes in IR will correlate with changes in fitness and IHTG.

Aim 2: Determine the post-intervention effects of HIIT on IHTG, and CVD and IR markers 3 months after completion of the HIIT in adolescents with baseline NAFLD.

2A. Quantitate the change in IHTG percent. Hypothesis: HIIT will have a sustained positive effect on IHTG, and that IHTG 3-months post-HIIT will be significantly lower compared to baseline level.

2B. Estimate changes on IR and other CVD markers. Hypothesis: HIIT will have a sustained positive effect on IR, and that IR 3-months post-HIIT will be significantly lower compared to baseline level.

Pediatric NAFLD has serious cardio-metabolic health outcomes. Findings of this study will inform clinical providers in the use of HIIT as a modality to treat adolescent NAFLD and associated morbidities, and produce preliminary data for mechanistic studies to probe pathways implicated in the pathogenesis of NAFLD.

Preliminary Results

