We propose a 4-week HIIT intervention in adolescents (ages 13 to 18, inclusive) with NAFLD. Up to 150 adolescents at-risk for NAFLD will be recruited to be able identify enough number of subjects with NAFLD (prevalence of NAFLD in our cohort was 40%; see data analysis section below). Our goal is to have 46 subjects with NAFLD to complete the study. Subjects will be randomized to either an exercise group or control group at a 5:1 ratio.

Because the objective of the study is to assess the effect of exercise in hepatic steatosis, we will use a multi-step approach to identify subjects with NAFLD and without disqualifiers (see

[figure not shown]

Figure 2. Study Design. FMD, Flow-Mediated Dilation; DXA, Dual X-Ray Absorptiometry; OGTT, Oral Glucose Tolerance Test; MRI, Magnetic Resonance Imaging; ACNC, Arkansas Children’s Nutrition Center; HIIT, High-Intensity Interval Training. *These assessments will only be completed if Visit 5 takes place at ACNC. Note: Physical Activity (PA) assessment via FitBit will also be conducted throughout the study.

exclusion criteria). When available, electronic medical records will be reviewed to identify potential participants. Eligibility will be assessed using a screening form. Potential participants may be screened over the phone or in person. If determined eligible, potential participants will be invited to attend a study visit. Study visits will take place at the Arkansas Children’s Nutrition Center (ACNC) and/or Arkansas Children’s Hospital. Parents and/or participants will be instructed not to come to the study visit and other assessments if parent and/or participant is ill. The visit/assessments will be rescheduled if that is case to a time when parents and participants are well and asymptomatic. **Figure 2** summarizes the study visit schedule for the exercise and control groups as described in detail below.

Participants will be asked not to eat or drink anything (except water) after 10 pm the night prior to the study visits. Due to fasting, study visits will be scheduled in the morning. Study compensation will be provided via ClinCard and/or gift card(s). Lunch and/or snacks may be offered to participants and/or parents at study visits.

Baseline/Pre-Intervention: All Subjects

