As an exploratory aim, diagnostic performance of FibroScan for the NAFLD adolescent will be determined by discriminating NAFLD status defined by FibroScan against that by MRI to calculate sensitivity, specificity, positive and negative predictive values. Additional agreement statistics such as concordance correlation coefficient and Bland-Altman plots will be provided for the continuous measurements of IHTG levels measured by both methods.

In our pilot data, the IHTG levels were 11.5 ± 5.4 percent at baseline for NAFLD subjects (N=23). With a pre-defined clinically significant change of 20% relative decrease from baseline, we expect the NAFLD subjects' fat percent will be decreased to an average of 9.2 ± 5.4 percent after HIIT intervention, which is an equivalent effect size of 0.43. In order to detect this effect size at 80% power, we will need 38 NAFLD participants in the intervention group, therefore 8 NAFLD subjects in the control group. Accounting for a 20% dropout rate and false-negative screening from FibroScan, we propose to enroll 58 subjects with NAFLD. Therefore, we need to screen no less than 150 subjects at-risk for NAFLD at baseline, to be able to identify 58 subjects with NAFLD (NAFLD prevalence was 40% in our pilot study, see preliminary data section above).

Ethical Considerations

This study will be conducted in accordance with all applicable government regulations and the University of Arkansas for Medical Sciences research policies and procedures. This protocol and any amendments will be submitted and approved by the UAMS Institutional Review Board (IRB) to conduct the study.

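### The 80% power is built on the HIIT arm's own fall in IHTG; for the randomised HIIT-versus-control comparison in Aim 1A, 38 against 8 gives about 19% two-sided (29% one-sided) if the SD of change is 5.4 and controls do not change

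*Combined protocol and SAP*

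**What the plan says.** The sample-size paragraph of Data Analysis starts from a pilot IHTG of 11.5 ± 5.4 percent in 23 subjects with NAFLD. The target is set this way: "With a pre-defined clinically significant change of 20% relative decrease from baseline". IHTG is therefore expected to be "decreased to an average of 9.2 ± 5.4 percent after HIIT intervention", which the plan converts to an effect size of 0.43. It continues: "In order to detect this effect size at 80% power, we will need 38 NAFLD participants in the intervention group", and "therefore 8 NAFLD subjects in the control group". The paragraph names no test, alpha, sidedness, SD of change or expected change in controls.

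Study Design and Procedures gives the matching totals: "Our goal is to have 46 subjects with NAFLD to complete the study", and "Subjects will be randomized to either an exercise group or control group at a 5:1 ratio".

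The hypothesis under Aim 1A (Objective/Specific Aims) is: "IHTG will decrease after HIIT, and the change will be greater than that seen in controls". Data Analysis says the effect of HIIT will be assessed by comparing changes between the groups in a linear mixed model with group, visit and their interaction. Its last sentence assigns to Aim 1 a contrast between the 5-week and baseline visits, without saying that this contrast is to be taken between groups.

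**The concern.** The quantity that was powered is not the quantity that the randomised comparison tests. The 0.43 describes how far the HIIT arm moves from its own baseline. Aim 1A asks whether that movement exceeds the movement in controls, so the sampling error of only 8 controls enters the test and dominates its standard error.

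IHTG is the primary outcome and Aim 1A is the trial's only randomised comparison on it, so readers are likely to attach the 80% to that test. If HIIT produced exactly the pre-defined 20% reduction, the between-arm test would miss it about four times in five (two-sided, SD of change 5.4, no change in controls). Without a corrected statement, such a miss could be reported as an adequately powered negative finding.

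**Working it through.** **Inputs from the plan.** Baseline mean 11.5 and SD 5.4; target fall 20% × 11.5 = 2.3 points; 38 HIIT and 8 control completers; 5:1 allocation (38/5 = 7.6, rounded to 8).

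**Assumptions, because the plan is silent.** Alpha 0.05, shown one- and two-sided; no change in controls; the same SD of change in both arms. The SD of change is 5.4 × √(2(1 − ρ)), where ρ is the pre-post correlation. It equals 5.4 when ρ = 0.5. All power figures use the noncentral t distribution.

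**Step 1: where the 38 comes from.** The effect size is 2.3/5.4 = 0.426, printed as 0.43. Sizes for 80% power at SD of change 5.4:

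| Test | One-sided | Two-sided |
|---|---|---|
| Paired t, HIIT arm only | 36 | 46 |
| Two-sample t, 1:1 | 69 per arm | 88 per arm |
| Two-sample t, 5:1 | 210 + 42 | 265 + 53 |

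Only a within-arm test comes near 38. With n = 38, the paired t-test has 82% power one-sided and 72% two-sided. A one-sided signed-rank test, sized as 36 × π/3 = 37.7, would give exactly 38, but the plan does not mention it. The two-sided 46 equals the planned total of completers (46 × 5/6 = 38.3 in the HIIT arm), not the HIIT arm itself. That the 80% refers to a within-arm test is therefore an inference, though no between-arm test fits the printed inputs.

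**Step 2: between-arm power at SD of change 5.4.**

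- Standard error = 5.4 × √(1/38 + 1/8) = 5.4 × 0.389 = 2.10.
- Noncentrality = 2.3/2.10 = 1.09, with 38 + 8 − 2 = 44 degrees of freedom.
- Power = 18.8% two-sided and 28.5% one-sided. A simulation of 40,000 runs gave 19.0% and 28.6%.
- 95% CI half-width = 2.015 × 2.10 = 4.23 points, against a target difference of 2.3.
- Difference detectable with 80% power = 6.0 points two-sided (6.0/11.5 = 52% of baseline) or 5.3 one-sided.

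**Step 3: sensitivity to the unstated correlation (38 vs 8, 2.3 points).**

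| ρ | Two-sided power | One-sided power |
|---|---|---|
| 0 | 12% | 19% |
| 0.3 | 15% | 23% |
| 0.5 | 19% | 29% |
| 0.6 | 22% | 33% |
| 0.7 | 28% | 40% |
| 0.8 | 40% | 52% |
| 0.9 | 67% | 78% |
| 0.95 | 92% | 96% |

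Power reaches 80% at ρ of about 0.93 two-sided or 0.91 one-sided. The two-sided detectable difference is 3.8 points at ρ = 0.8 and 2.7 at ρ = 0.9, with 95% CI half-widths of 2.7 and 1.9.

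**Step 4: a check that does not depend on choosing 5.4.** For any SD of change, the between-arm standard error is √(1 + 38/8) = 2.40 times the within-arm one. Choose the SD so that 38 gives exactly 80% within the HIIT arm: 4.93 two-sided or 5.60 one-sided. Between-arm power is then 22% or 27%. At the correlation of about 0.93 that would bring the two-sided between-arm test to 80%, within-arm power exceeds 99.99%, so 38 would no longer be the number needed for 80%.

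**The case against.** The strongest reply is that 5.4 is a cross-sectional SD. Nothing in the plan supports a correlation of 0.5 in particular, and at 0.95 the between-arm test would have 92% power. That is a fair reason to give a range and not one number. It does not rescue the stated 80%, because any SD of change that makes 38 the right size for a within-arm test leaves 22% to 27% between arms (Step 4).

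A second reply is that sizing on the HIIT arm has a legitimate use. The first half of the Aim 1A hypothesis is a within-arm claim. Aim 2A compares 3-month IHTG with baseline, and only the exercise group attends that visit. The sample-size paragraph also ties its 80% to the intervention group and makes no explicit claim about a between-arm test. All of this stands. It explains the choice, but it does not supply power for the second half of Aim 1A or for the between-group analysis that the plan specifies.

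Third, the printed arithmetic is sound: 2.3/5.4, 38/5 and 46/0.8 = 57.5, rounded to 58, all work. That is also right. The fault is a mismatch between what was sized and what will be tested, not a slip in calculation.

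**Conclusion.** The concern holds and must be fixed. The stated 80% does not apply to the HIIT-versus-control comparison of IHTG change, and no power is stated for that comparison. With 38 and 8 completers it is about 19% two-sided or 29% one-sided for a 2.3-point difference, given alpha 0.05, no change in controls and an SD of change of 5.4 in both arms. Power is below 80% unless the pre-post correlation exceeds about 0.93 (0.91 one-sided). Any fall in the control group would shrink the difference and lower power further.

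Two matters remain uncertain: which test produced the 38, and the true SD of change. Neither alters the conclusion that the within-arm 80% cannot be carried over to the between-arm test.

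**What to change.** **1. Sample-size paragraph.** Name the test behind the 80%, with its alpha, sidedness and SD of change, and recompute the 38 from those inputs. Then add the between-arm statement, substituting the sponsor's own SD of change if one can be justified. For example:

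> For the HIIT-versus-control difference in IHTG change with 38 and 8 completers (two-sided alpha 0.05, no change in controls, SD of change 5.4), power for a 2.3-point difference is about 19%, and the difference detectable with 80% power is about 6.0 points. Power is 12% to 67% over pre-post correlations from 0 to 0.9.

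State also that a non-significant between-arm result will be reported as inconclusive, with its confidence interval.

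**2. Analysis paragraph.** Define the Aim 1 test as the two-sided group-by-visit contrast: 5-week minus baseline, HIIT minus control. Report its 95% CI and label the within-HIIT change as supportive. Aim 1A and the interaction term already imply this contrast; only the last sentence leaves it open.

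**3. Recommended, not essential.** Adjust the contrast for baseline IHTG and for sex, the blocking factor. Baseline is a response in the planned model, so this needs an ANCOVA or a constrained-baseline model. With residual SD 5.4 × √(1 − ρ²) and 42 degrees of freedom, two-sided power rises from 19% to 24% at ρ = 0.5 and from 40% to 43% at ρ = 0.8.

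**4. Minor.** Reconcile the pilot figures: 11.5 with N = 23 in Data Analysis, against 11 with n = 24 in Table 1 of Preliminary Results.

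**Cost.** Protocol wording and model code. Enrolment, allocation and visits do not change. The price is a less favourable stated power for Aim 1.
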